## 12.4 Response Criteria

### 12.4.1 Evaluation of Target Lesions

Complete Response (CR): Disappearance of all target lesions. Any pathological lymph nodes (whether target or non-target) must have reduction in short axis to <10 mm.

Partial Response (PR): At least a 30% decrease in the sum of the diameters of target lesions, taking as reference the baseline sum diameters.

Progressive Disease (PD): At least a 20% increase in the sum of the diameters of target lesions, taking as reference the smallest sum on study (this includes the baseline sum if that is the smallest on study). In addition to the relative increase of 20%, the sum must also demonstrate an absolute increase of at least 5 mm. (Note: the

appearance of one or more new lesions is also considered progressions).

Stable Disease (SD): Neither sufficient shrinkage to qualify for PR nor sufficient increase to qualify for PD, taking as reference the smallest sum diameters while on study.

#### 12.4.2 Evaluation of Non-Target Lesions

Complete Response (CR): Disappearance of all non-target lesions and normalization of tumor marker level. All lymph nodes must be non-pathological in size (<10 mm short axis). Note: If tumor markers are initially above the upper normal limit, they must normalize for a patient to be considered in complete clinical response.

Non-CR/Non-PD: Persistence of one or more non-target lesion(s) and/or maintenance of tumor marker level above the normal limits.

Progressive Disease (PD): Appearance of one or more new lesions and/or *unequivocal progression* of existing non-target lesions. *Unequivocal progression* should not normally trump target lesion status. It must be representative of overall disease status change, not a single lesion increase.

Although a clear progression of “non-target” lesions only is exceptional, the opinion of the treating physician should prevail in such circumstances, and the progression status should be confirmed at a later time by the review panel (or Principal Investigator).

#### 12.4.3 Evaluation of Best Overall Response

The best overall response is the best response recorded from the start of the treatment until disease progression/recurrence (taking as reference for progressive disease the smallest measurements recorded since the treatment started). The patient's best response assignment will depend on the achievement of both measurement and confirmation criteria.

#### For Patients with Measurable Disease (i.e., Target Disease)

Target Lesions	Non-Target Lesions	New Lesions	Overall Response	Best Overall Response when Confirmation is Required*
CR	CR	No	CR	>4 wks. Confirmation**

CR	Non-CR/Non-PD	No	PR	$\geq 4$ wks. Confirmation**
CR	Not evaluated	No	PR	
PR	Non-CR/Non-PD/not evaluated	No	PR	
SD	Non-CR/Non-PD/not evaluated	No	SD	Documented at least once $\geq 4$ wks. from baseline**
PD	Any	Yes or No	PD	no prior SD, PR or CR
Any	PD***	Yes or No	PD	
Any	Any	Yes	PD	

* See RECIST 1.1 manuscript for further details on what is evidence of a new lesion.
 
** Only for non-randomized trials with response as primary endpoint.
 
*** In exceptional circumstances, unequivocal progression in non-target lesions may be accepted as disease progression.
 
Note: Patients with a global deterioration of health status requiring discontinuation of treatment without objective evidence of disease progression at that time should be reported as "symptomatic deterioration." Every effort should be made to document the objective progression even after discontinuation of treatment.
				

### For Patients with Non-Measurable Disease (i.e., Non-Target Disease)

Non-Target Lesions	New Lesions	Overall Response
CR	No	CR
Non-CR/non-PD	No	Non-CR/non-PD*
Not all evaluated	No	not evaluated
Unequivocal PD	Yes or No	PD
Any	Yes	PD

* 'Non-CR/non-PD' is preferred over 'stable disease' for non-target disease since SD is increasingly used as an endpoint for assessment of efficacy in some trials so to assign this category when no lesions can be measured is not advised
		

#### 12.4.4 Duration of Response

Duration of overall response: The duration of overall response is measured from the time measurement criteria are met for CR or PR (whichever is first recorded) until the

first date that recurrent or progressive disease is objectively documented (taking as reference for progressive disease the smallest measurements recorded since the treatment started).

The duration of overall CR is measured from the time measurement criteria are first met for CR until the first date that progressive disease is objectively documented.

Duration of stable disease: Stable disease is measured from the start of the treatment until the criteria for progression are met, taking as reference the smallest measurements recorded since the treatment started, including the baseline measurements.

Treatment beyond progression: Subjects who continue treatment beyond initial investigator-assessed, RECIST 1.1-defined progression will be considered to have investigator-assessed progressive disease at the time of the initial progression event.

### **13.0 CRITERIA FOR REMOVAL FROM STUDY**

- Disease progression on treatment with nivolumab and ipilimumab.
- Patients may be removed from the study for protocol non-compliance.
- If at any time the patient develops unacceptable toxicity he/she will be removed from study.
- A patient can be removed from the trial if a dose delay of > 6 weeks occurs, unless the PI deems it appropriate to keep the patient on the trial as per protocol guidelines (see Section 11).
- Participants can be removed from the study at any time if the study doctor feels that it is in their best interest to do so.
- Patients may withdraw consent from the study at any time.

#### **Treatment Beyond Progression**

Accumulating evidence indicates a minority of subjects treated with immunotherapy may derive clinical benefit despite initial evidence of PD.

Subjects will be permitted to continue treatment beyond initial RECIST 1.1 defined PD as long as they meet the following criteria:

- Investigator-assessment that continued protocol therapy could elicit future clinical benefit and the subject is tolerating study treatment.

The assessment of clinical benefit should take into account whether the subject is clinically deteriorating and unlikely to receive further benefit from continued treatment.

Followup imaging to evaluate for further progression will be performed 4-8 weeks after the initial scan demonstrating disease progression. Subsequent scans may be performed every 8 weeks (+/- 1 week) or every 12 weeks (+/- 1 week) per the investigator's discretion. Subjects should discontinue study therapy upon evidence of further progression, defined as an additional 10% or greater increase in tumor burden volume from time of initial progression (including all target lesions and new measurable lesions).

New lesions are considered measurable at the time of initial progression if the longest diameter is at least 10 mm (except for pathological lymph nodes, which must have a short axis of at least 15 mm) and was not present during baseline scan. Any new lesion considered non-measurable at the time of initial progression may become measurable and therefore included in the tumor burden measurement if the longest diameter increases to at least 10 mm (except for pathological lymph nodes, which must have an increase in short axis to at least 15 mm).

#### **14.0 BIOSTATISTICS**

The primary endpoint of the study for each cohort is best overall response rate (BOR; CR+PR by RECIST v1.1). The ACC (Cohort 1) and non-ACC cohorts (Cohort 2) will be assessed separately. For ACC, our recent literature review of all systemic chemotherapy studies reported for R/M ACC patients from 1966 to 2009 revealed that these were generally small studies of variable, poor methodological quality from which definitive conclusions regarding the efficacy of chemotherapy are impossible to establish. Objective responses with cytotoxic chemotherapy were infrequent, and in 10 studies evaluating different targeted agents (imatinib, gefitinib, cetuximab, lapatinib, bortezomib (excluding the VEGR targeted TKIs)) involving 157 ACC patients, only 2 objective responses were reported (in response to high dose imatinib). Notably, there is no data addressing potential efficacy of systemic therapy beyond the first line setting in R/M ACC. The same concerns regarding trial design and modest activity with chemotherapy apply to non-ACC histologies as well. There currently is no standard therapy for SGs. Therefore, we will adopt a BOR of 5% as the null hypothesis and a BOR of 20% as desirable. A minimax two-stage design will be used for each cohort. In order to detect a difference between an unacceptable ORR of 5% and a desirable ORR of 20% with a one-sided type I error of 10% and power of 90%, at least 1 response needs to be observed among the first 18 patients enrolled in the first stage. If this is achieved, then the study will progress to the second stage in which an additional 14 patients will be accrued. In order to move to the second stage of the study, the patient response in the first stage must occur within 6 cycles (or 36 weeks (+/- 2 weeks)) of drug treatment. At the end of the trial, at least 4 responses need to be observed among a total of 32 patients of the cohort to be considered worthy of further investigation. Maximum number of patients treated in both cohorts combined would be 64 patients.

Given the length of the observation period for response, if the decision on whether to proceed to the second stage cannot be made after the first 18 patients have been enrolled, the study will not halt and patients will continue to be enrolled. In the worst case scenario, all 32 patients will have been enrolled before the decision on whether to proceed to the second

stage can be made. In this case the study becomes a single-stage design in effect, which has the same type-I error rate, power, and rejection criterion for the null hypothesis as the original minimax two-stage design.

Patients who receive at least one dose of either study medication (nivolumab or ipilimumab) will be included in the evaluation of the primary objective. Patients who are enrolled, but withdraw consent or are removed from the study prior to obtaining the first response assessment while on study treatment can be replaced, except for those who were taken off study for progression of disease or toxicity (in these specific incidences, patients will be classified as non-responders).

Secondary endpoints will include measuring progression-free survival (PFS) with recurrent/metastatic SGC treated with nivolumab and ipilimumab, and assessing the safety/tolerability of the regimen.

PFS will be estimated using Kaplan-Meier methodology, with time origin at the start of the treatment. Patients will be followed until progression of disease or death related to disease, whichever come first. Patients removed from the study for reasons unrelated to the disease (e.g. moving, accidental death) will be counted as censored. Patients who continue treatment beyond initial investigator-assessed, RECIST 1.1-defined progression, and are subsequently removed from study within the next radiographic assessment for progression, will be considered to have investigator-assessed progressive disease at the time of the initial progression event.

Safety will be assessed in terms of AEs, laboratory data and vital sign data, which will be collected for all patients. Appropriate summaries of these data will be presented. AEs will be listed individually per patient according to CTCAE version 4.0, and the number of patients experiencing each AE will be summarized. The safety population will comprise all patients who receive at least one dose of study treatment.

Due to the limited sample size, the analyses investigating the association between correlative markers and BOR will be exploratory. These exploratory analyses will be evaluated within each cohort separately. Categorical markers will be correlated with BOR by Fisher's exact tests. Continuous markers will be correlated with BOR by logistic regression. Immune activation that occurs concomitant with experimental therapy will be serially assessed in the PBMC analysis performed for each patient. Specifically, the changes in T cell subsets that occur with therapy will be analyzed and interpreted as potential indicators of immune activation induced by drug therapy. Proportions of T cell subsets will be calculated with 95% confidence intervals at each time point and plotted over time to reveal any trend. The baseline proportions of T cell subset and changes in these proportions from baseline to last time point will be correlated with the response status univariately.

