## 10.0 EVALUATION DURING TREATMENT/INTERVENTION

All evaluations/tests and research collections may be performed up to 3 days prior to the patient being treated.

Cycle/Week of Therapy (1 cycle= 6 weeks)	Pre-Study a	Cycle 1 Week 1 i	Cycle 1 Week 3	Cycle 1 Week 5	Cycle 2+ f Week 1	Cycle 2+ f Week 3	Cycle 2+ f Week 5	Off Study g
Weeks on study	-	1	3	5	7	9	11	-
Nivolumab b		X	X	X	X	X	X	
Ipilimumab b		X			X			
Informed consent	X							
Concurrent meds	X	X d	X	X	X			X
Physical exam	X	X d	X	X	X			X
Vital signs (pulse, blood pressure)	X	X d	X	X	X			X
Weight	X	X d	X	X	X			X
Adverse event evaluation	X	X d	X	X	X			X
CBC w/diff, plts	X	X e	X	X	X	X	X	X
Comprehensive panel c	X	X e	X	X	X	X	X	X
TSH	X				X			X
Beta-HCG (serum or urine)	X i							
Request for archival tumor tissue	X							
Research blood draw	X							
Research tumor biopsies k	X k		X k					
Research peripheral blood collection j		X			X			X
Tumor measurements h	X	CT and/or MRI will be performed every 12 weeks (+/- 1 week) (or approximately every 2 cycles). Objective responses should be confirmed with a second assessment performed at least 4 weeks later.						

a: See Section 8.0 for the timing of these tests/evaluations prior to the start of therapy.

b: Study drugs will be administered at the following doses/schedules: nivolumab 3 mg/kg IV every 2 weeks and ipilimumab 1 mg/kg IV every 6 weeks. At the investigator's discretion patients can be treated with nivolumab alone after 4 cycles for safety concerns.

c: Albumin, alkaline phosphatase, total bilirubin, bicarbonate, BUN, calcium, chloride, creatinine, glucose, potassium, total protein, SGOT [AST], SGPT [ALT], sodium.

d: These Week 1 evaluations maybe performed within 3 days prior to the start of treatment.

e: These Week 1 laboratory tests may be done up to 7 days prior to starting treatment. It is unnecessary to repeat these laboratory tests if the screening assessments of the same tests were performed within 7 days prior to the first dose of therapy.

f: These columns reflect the schedule of assessments/treatment required for Cycle 2 and subsequent cycles in the weeks designated.

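### A first-stage response counts for continuation only within 36 weeks, while the final rule has no time limit: a small, avoidable loss of power when the stage-1 stop operates

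*Combined protocol and SAP*

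**What the plan says.** Section 14.0 sets up each cohort to "adopt a BOR of 5% as the null hypothesis and a BOR of 20% as desirable", "with a one-sided type I error of 10% and power of 90" per cent. To continue, "at least 1 response needs to be observed among the first 18 patients enrolled in the first stage"; then "an additional 14 patients will be accrued". At the end, "at least 4 responses need to be observed among a total of 32 patients of the cohort".

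One condition applies to the first look only: "the patient response in the first stage must occur within 6 cycles (or 36 weeks (+/- 2 weeks)) of drug treatment". The final rule carries no such condition, and Section 12.4.3 has none either: "The best overall response is the best response recorded from the start of the treatment until disease progression/recurrence".

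Three other provisions bear on the point.
- Section 14.0 does not pause enrolment while the first-stage decision is pending. If all 32 patients are in before the decision, the cohort is treated as a single-stage design with the same final criterion.
- Section 10.0 schedules scans every 12 weeks and adds: "Objective responses should be confirmed with a second assessment performed at least 4 weeks later".
- Section 12.4.4 times the duration of response from the point at which the measurement criteria are first met.

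**The concern.** The 18 + 14 design and its 90% power rest on one response definition at both looks. The plan uses two. A first response at the week-48 scan in one of the first 18 patients counts toward the final 4 but cannot open stage 2, even when it is already on file at the decision.

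That can easily happen. At 1 to 1.5 patients per cohort per month, the first patient has about 85 to 110 weeks of follow-up when patient 18 reaches week 36. Because the gate is a single response, a cohort whose only known responses are late would be closed as inactive. What is at stake is a somewhat higher chance of stopping an active regimen, in a design with almost no spare power.

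**Working it through.** **Inputs.** From Section 14.0: p0 = 5%, p1 = 20%, n1 = 18 (continue on at least 1 response), n2 = 14, success on at least 4 of 32, window 36 (±2) weeks. From Section 7.0: accrual of 2 to 3 patients per month for the whole study. Assumed, because the documents do not say: f, the share of responses first seen after week 36; response timing independent between patients; and accrual split evenly, so 1 to 1.5 per cohort per month.

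**Step 1: the plan's own figure.** Let X1 ~ Bin(18, p) and X2 ~ Bin(14, p).

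P(success) = Σ over x ≥ 1 of P(X1 = x) · P(X2 ≥ 4 − x).

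- p = 5%: type I error 7.21%.
- p = 20%: power 90.15%.
- Stopping at stage 1 when p = 20%: 0.8^18 = 1.8%.

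The stated 10% and 90% are met, with 0.15 points of power to spare.

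**Step 2: the 36-week limit, stop always enforced.** A cohort with x stage-1 responders fails the gate if all x are late, which has probability f^x. So

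Power(f) = Σ over x ≥ 1 of P(X1 = x) · (1 − f^x) · P(X2 ≥ 4 − x),

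and stopping at stage 1 when p = 20% has probability (1 − 0.2(1 − f))^18.

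For f = 10% the loss is:
- x = 1: 0.0811 × 0.1 × 0.5520 = 0.0045
- x = 2: 0.1723 × 0.01 × 0.8021 = 0.0014
- x = 3: 0.2297 × 0.001 × 0.9560 = 0.0002

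The total is about 0.6 points, so power is 89.5%.

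| Late share f | Stop at stage 1, p = 20% | Power |
|---|---|---|
| 0% | 1.8% | 90.15% |
| 10% | 2.8% | 89.5% |
| 20% | 4.3% | 88.5% |
| 30% | 6.6% | 86.8% |

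Power crosses 90.0% at f = 3.0% and falls 2 points below 90% at about f = 23%. Type I error only falls (7.07% at f = 10%).

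**Step 3: the single-stage fallback.** If 14 more patients join a cohort in the 36 weeks after patient 18, only the 4-of-32 rule applies: power 90.69%, type I error 7.38%, whatever f is. Thirty-six weeks is 36/4.345 = 8.3 months, so about 8.3 further patients are expected at 1 per month and 12.4 at 1.5. With Poisson accrual, P(14 or more) = w is about 4% and 36%. Then

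Power = w × 90.69% + (1 − w) × Power(f).

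At 1.5 per month and f = 10%: 0.363 × 90.69 + 0.637 × 89.54 = 89.96%.

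| Accrual per cohort | f = 10% | f = 20% | f = 30% | 90% crossed at |
|---|---|---|---|---|
| 1 per month | 89.6% | 88.6% | 86.9% | f ≈ 3.6% |
| 1.5 per month | 89.96% | 89.3% | 88.2% | f ≈ 9% |

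A cohort accruing 2 per month crosses 90% only at about f = 25%. Using the +2-week allowance (38 weeks) moves the crossing at 1.5 per month to about 11%.

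**Step 4: the limit removed, decision date unchanged.** A simulation with the fallback included, at 1 and 1.5 patients per cohort per month and late responses placed at weeks 48 and 60, regains about 0.3–0.5, 0.8–1.3 and 1.6–2.8 points of power at f = 10%, 20% and 30%. Not all of the loss returns, because some late responses occur after the decision date.

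**The case against.** A fixed window for an interim endpoint is a legitimate prespecified choice, and this one takes in three scheduled scans. Late first-stage responses are not lost altogether: they still count toward 4 of 32 if the cohort continues. The limit changes the outcome only when every stage-1 responder is late and fewer than 32 patients are enrolled. The 3% crossing is close to a rounding effect, and the remedy does not guarantee 90% at every late share either. All of this stands, and it keeps the point small.

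Three stronger readings are tempting, and the documents do not support them.

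- *That the protocol itself expects late responses of this kind.* Its remarks on delayed response (Sections 1.0, 4.2 and 9.3.6) concern responses after a short period of progression. Section 12.4.3 counts best response only up to progression and Section 12.4.4 dates progression at the initial event, so those responses count at neither look. They say nothing about first responses after week 36.
- *That a response first seen at week 36 is lost because it cannot be confirmed before week 40.* Nothing requires confirmation inside the window. Section 14.0 speaks of when the response occurs, and Section 12.4.4 supports dating it from first measurement. The text is silent rather than wrong, and a clarifying phrase is enough.
- *That power falls below 90% at 3% late under all conditions.* That figure ignores the no-halt provision.

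**Conclusion.** The point holds in a limited form. The two looks use different response windows, and when the stage-1 stop operates, known responses after week 36 are ignored for continuation.

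If 10% of responses are late, power is 89.5% with the stop always enforced and about 89.6% to 90.0% with the fallback included. At 30% late it is 86.8%, or 86.9% to 88.2% with the fallback. If all 32 patients are enrolled before the decision there is no effect at all (power 90.7%).

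These sizes rest on an assumed late share, independent response times, Poisson accrual and an even split between cohorts. The documents fix none of these, so a material loss is possible but not shown.

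Type I error is not a concern. A reader might infer that 7.2% is a ceiling. It is 7.4% under the fallback, still well inside 10%.

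**What to change.** In Section 14.0, keep the decision date at the point when patient 18 reaches week 36 and delete the per-patient limit. Count every response in the first 18 patients first documented by that date. State that a response is dated from when the measurement criteria are first met and that confirmation may follow.

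This is a change to one or two sentences. It adds no patients and no delay, and type I error stays at or below about 7.4%.

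If the 36-week limit is kept, say that the 90% power assumes essentially no later responses, give the power for a plausible late share, and state whether confirmation must fall inside the window.

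### Section 14 puts every dosed patient in the primary evaluation but also lets some dosed early leavers be replaced, without saying how they count toward 18 and 32 or how the cap of 64 allows for them

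*Combined protocol and SAP*

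**What the plan says.** Section 14.0 (Biostatistics) defines the primary population by exposure: "Patients who receive at least one dose of either study medication (nivolumab or ipilimumab) will be included in the evaluation of the primary objective". Section 12.1 agrees, since it makes a patient with measurable disease at baseline and one dose evaluable for response.

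The following sentence of Section 14.0 deals with early leavers. It covers enrolled patients whose consent is withdrawn and, on the same terms, anyone "removed from the study prior to obtaining the first response assessment while on study treatment can be replaced". There is one carve-out, which shields two kinds of exit from this rule: all early leavers fall under it "except for those who were taken off study for progression of disease or toxicity". Patients in the excepted group are classified as non-responders. No classification is given for the rest.

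The same section fixes three counts:

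- Stage 1: "at least 1 response needs to be observed among the first 18 patients enrolled in the first stage".
- Final rule: "at least 4 responses need to be observed among a total of 32 patients of the cohort to be considered worthy of further investigation".
- Exposure: "Maximum number of patients treated in both cohorts combined would be 64 patients".

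Two other places bear on the point. Section 13.0 allows discretionary removal: "Participants can be removed from the study at any time if the study doctor feels that it is in their best interest". Section 10.0 schedules the first on-treatment scan at about 12 weeks and adds: "Objective responses should be confirmed with a second assessment performed at least 4 weeks later". Section 12.4.3 likewise makes best response depend on confirmation.

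**The concern.** Replacement is not restricted to patients who were never dosed. The reference to being on study treatment and the exception for toxicity both show that dosed patients are in scope. Take a patient who receives several infusions and withdraws consent in week 8. Under one sentence that patient belongs to the primary evaluation. Under the next, another patient may be enrolled in that place. The plan does not say whether the first patient stays in the denominator, is a non-responder, or counts toward the 18 or the 32.

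The primary endpoint of each cohort is a proportion, so two candidate denominators (32, or 32 plus the number replaced) give two results, and the choice could be made after responses are known. The trial is open-label and some removals are at the investigator's discretion. Leaving out patients removed for reasons related to how they were doing would push the reported rate upward. The number of patients exposed is also at stake, because the stated maximum leaves no room for any dosed replacement once both cohorts are full.

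**Working it through.** **Inputs from Section 14.0.** Null rate 5%, target 20%, one-sided type I error 10%, power 90%. Stage 1 has 18 patients and continues with at least 1 response. Stage 2 adds 14, for 32 in total, and success is at least 4 responses. The maximum treated is 64.

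**Assumption.** k is the number of dosed patients replaced per cohort. The documents give no dropout rate, so k is varied.

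**1. The plan's own design.** The probability of success at response rate p is

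P(p) = Σ (x = 1 to 18) Bin(x; 18, p) × Pr[Bin(14, p) ≥ 4 − x].

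- Two-stage: P(0.05) = 0.0721 and P(0.20) = 0.9015.
- Single-stage with 32 patients and a cut-off of 4 (the fallback that the section describes): 0.0738 and 0.9069.

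Both meet the 10% bound and the 90% target. The sample size and cut-off are correct.

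**2. Number treated.** 2 × 32 = 64 holds only with no dosed replacements. In general, with both cohorts full, the number is 2 × (32 + k) = 64 + 2k:

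- k = 1: 66
- k = 2: 68
- k = 3: 70

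**3. Reported rate with 4 responders, leavers kept.** This is 4/(32 + k):

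- k = 0: 4/32 = 12.5%
- k = 1: 4/33 = 12.1%
- k = 2: 4/34 = 11.8%
- k = 3: 4/35 = 11.4%

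**4. The final decision.** Suppose leavers contribute no confirmed response and 32 patients who stay are observed. The count compared with 4 is then the same whether leavers are kept or dropped.

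- If the 5% null describes those who stay, type I error remains 0.072 (two-stage) or 0.074 (single-stage) for any k.
- If the 5% null describes all dosed patients, the rate among those who stay is 0.05 × (32 + k)/32. The error (two-stage / single-stage) becomes 0.079 / 0.081 at k = 1, 0.086 / 0.088 at k = 2, 0.093 / 0.095 at k = 3 and 0.101 / 0.103 at k = 4. It first passes 10% at k = 4.

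**5. Stage 1.** If k leavers count among the first 18, and 32 others are still followed in total, stage 1 has 18 − k patients who can respond. Power at 20% goes from 0.901 to 0.899 with one leaver and 0.891 with three.

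**6. If dosed patients could not be replaced.** Then 32 − k patients can respond. Two-stage power depends on whether the leavers fall in stage 1 (lower figure) or stage 2 (upper figure). With 20% among those who stay:

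- k = 1: 0.886 to 0.888
- k = 2: 0.869 to 0.874
- k = 3: 0.849 to 0.857

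If 20% instead refers to all dosed patients, the rate among those who stay is 0.20 × 32/(32 − k), and power remains between 0.90 and 0.91 for k up to 4.

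**The case against.** The best defence is that the population is defined. Sections 14.0 and 12.1 both point to all dosed patients. Permission to replace is accrual wording, and nothing says that a replaced patient leaves the analysis. This stands to the extent that it would be wrong to say the plan has no denominator. The plan states one and then adds a sentence that conflicts with it. The defence does not close the gap, because only progression and toxicity leavers are called non-responders. That leaves open the reading that the others are dropped and replaced.

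Second, the affected group is narrow. The two exits most directly linked to outcome already count as failures. What remains is withdrawal, non-compliance or discretionary removal before about week 12. This also stands. A reader might infer that the reported rate is certainly biased upward. The documents do not show that: it depends on why these patients leave, and upward bias is only plausible.

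Third, the numbers are small. The exact 95% interval for 4/32 runs from about 3.5% to 29%, so a move from 12.5% to 11.4% lies well inside sampling error. A reader might also infer that the type I error is broken. It is not: 10% is exceeded only if the null is read over all dosed patients and at least four are replaced in a cohort.

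Finally, the unchanged response count rests on leavers having no confirmed response. The replacement sentence can be read so that a scan taken off treatment is not excluded. The assumption is reasonable for patients off study, but it is an assumption.

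**Conclusion.** The concern holds as an internal contradiction with a small numerical effect, and it should be fixed. The all-dosed population and the replacement of dosed patients are not reconciled with each other, with the counts of 18 and 32, or with the maximum of 64 treated. The conflict with the cap is plain arithmetic: one dosed replacement, with both cohorts otherwise full, exceeds it. The effect on the reported rate is about 1 percentage point with three replacements. The effect on the final decision at 4 responses is essentially nil if leavers have no confirmed response, and the stage-1 effect is at most 0.010 of power with three leavers. If no dosed patient is replaced, nothing changes. Every figure that depends on k rests on an assumed number of replacements.

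**What to change.** State in Section 14.0 that every dosed patient, replaced or not, stays in the response-rate denominator, and that any without a documented confirmed CR or PR counts as a non-responder. Then make the cap agree with the replacement rule in one of two ways:

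- **Limit replacement to patients who never received a dose.** 32 and 64 then stand. The plan should note that, if the 20% target refers to those who stay, two-stage power is about 0.89 with one early leaver and 0.85 to 0.86 with three.
- **Keep dosed replacement with the cut-off at 4.** Say whether replaced patients count among the first 18, and restate the maximum treated as 64 plus replacements.

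No numerical limit on replacements is needed. The cost is a short amendment, with either a slightly lower reported rate or a slightly lower stated power.
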